15.3 Assessment of Adverse Events

Each adverse event will be assessed for severity, causality, seriousness and expectedness as described below.

15.3.1 Severity

Severity or grading of AEs

Grade	Degree of Severity
1	Mild, with mild or no symptoms; no interventions required
2	Moderate; minimal intervention indicated; some limitation of activities
3	Severe but not life threatening; hospitalisation required; limitation of patient's ability to care for him/herself
4	Life threatening; urgent intervention required
5	Death related to adverse event

15.3.2 Causality

The assessment of relationship of adverse events to the administration of IMP is a clinical decision based on all available information at the time of the completion of the case report form.

The following categories will be used to define the causality of the adverse event:

Category	Definition
Definitely:	There is clear evidence to suggest a causal relationship, and other possible contributing factors can be ruled out.
Probably:	There is evidence to suggest a causal relationship, and the influence of other factors is unlikely
Possibly	There is some evidence to suggest a causal relationship (e.g. the event occurred within a reasonable time after administration of the trial medication). However, the influence of other factors may have contributed to the event (e.g. the participant's clinical condition, other concomitant events).
Unlikely	There is little evidence to suggest there is a causal relationship (e.g. the event did not occur within a reasonable time after administration of the trial medication). There is another reasonable explanation for the event (e.g. the participant's clinical condition, other concomitant treatments).
Not related	There is no evidence of any causal relationship.
Not Assessable	Unable to assess on information available.

15.3.3 Expectedness

Category	Definition
Expected	An adverse event which is consistent with the information about the IMP listed in the Investigator Brochure (or SPC if Licensed IMP) or clearly defined in this protocol.
Unexpected	An adverse event which is not consistent with the information about the IMP listed in the SPC * or clearly defined in this protocol.

* this includes listed events that are more frequently reported or more severe than previously reported

The reference document to be used to assess expectedness against the IMP is the SPC for Simvastatin 40mg film coated tablets (Sandoz Limited)

The following events listed below describe expected procedural related AEs:

- MRI is generally well tolerated. There can occasionally be some discomfort and/or claustrophobia.
- Discomfort from glare with optical imaging.

15.3.4 Seriousness

All events are assessed for seriousness as defined for an SAE in section 15.1.

15.4 Procedures for recording and reporting Serious Adverse Events

All serious adverse events (SAEs/SARs/SUSARs) will be recorded in the medical records and the CRF, and the sponsor's SAE log. The SAE log of SAEs will be reported to the sponsor at least once or twice per year in liaison with JRO Pharmacovigilance Manager.

All SAEs will be recorded from the time of the first enrolled participant's drug release (at Visit 2) until 6 weeks post-treatment (defined as six weeks beyond end of treatment).

All SAEs (except those specified in section 15.5 as not requiring reporting to the Sponsor), must be recorded on a serious adverse event (SAE) form. The CI/PI or designated individual will complete the sponsor's SAE form and email the form to the Sponsor at [contact] within 24 hours of his / her becoming aware of the event. The Chief or Principal Investigator will respond to any SAE queries raised by the sponsor as soon as possible.

Completed SAE forms must be sent within 24 hours of becoming aware of the event to the Sponsor
Email forms to [contact]

[figure not shown]
Reporting to the sponsor will be completed as per the sponsor's SOP and using the UCL SAE form (INV/S05) as amended for the trial.

SAE's will be reported to the sponsor until the end of the trial. SAR and SUSAR will need to be reported to the Sponsor irrespective of how long after IMP administration the reaction has occurred.

Participants must be followed up until clinical recovery is complete and laboratory results have returned to normal or baseline values, or until the event has stabilised. Follow-up should continue after completion of protocol treatment and/or trial follow-up if necessary.

Follow-up SAE forms (clearly marked as follow-up) should be completed and emailed to the JRO as further information becomes available.

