9.2 Visit 1 Screening/Baseline combined assessment (Day 0)

At this visit (which may be conducted over two days), the following will be assessed:

- Informed consent
- Medical History & Contraindications
- Physical examination & Medical review**
- Vital signs inc. pulse, blood pressure, temperature
- Concomitant medications
- EDSS disability assessment
- MSFC inc. 25FTW, 9HPT
- SDMT
- FAB
- Questionnaires (MSIS-29v2, MSWsv2, EQ5D5L)
- Safety Bloods (see section 11.1 for list of laboratory tests)
- Bloods for Immunology and biomarkers
- Urine pregnancy test for females of child bearing potential
- MRI inc. ASL / Questionnaire
- Modified Vascular Function Retinal Imaging Questionnaire
- Visual assessment (likely to take place on day 2 of this visit)
- Retinal Imaging (Advanced retinal imaging, OCT – likely to take place on day 2 of this visit)
- Full eligibility assessment

- Randomisation (see section 10)
- Drug dispensation at 40mg dose (see section 10.1) * .
- Drug diary issued
- Emergency telephone contact given

Participants will be advised on the administration of the medication and will be given a study specific patient card which will have study title, IMP details, patient ID and contact details of the out of hours contact in cases of emergency (see section 9.3.6). A drug diary will also be issued for participants to document compliance to IMP.

Participants will be reminded to bring the drug diary to the next visit.

This visit will take place across two sites. Visit 1 assessments will take place over two days, one for each site with the option to complete all assessments on one day if feasible. Randomisation and drug dispensation will take place on day 1 of visit 1.

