9.3 Follow-up assessments

9.3.1 Visit 2 (Week 4+1 week)

- Recording of AEs and concomitant medications
- Physical Examination & Medical Review**
- Vital signs inc. pulse, blood pressure, temperature
- Safety bloods (see section 11.1 for list of laboratory tests)
- Bloods for Immunology and biomarkers
- Drug compliance (pill count and drug diary review)
- Uptitration of drug at 80mg dose.
- MRI appointment for next visit booked/date confirmed with patient

- Retinal imaging appointment for next visit booked/date confirmed with patient
- Patient reminded to bring diary card, trial medication bottles with unused trial medication back for the next visit.

** Medical review will encompass any medical or MS-related symptoms that have arisen.

If a patient is unable to attend the clinic at week 4 or within the visit window, a TC will be arranged to check for AEs and acceptability to uptitrate and an appointment nearest to the timeframe will be scheduled.

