10.1 Treatment Schedule

The starting dose at baseline will be 40mg of Simvastatin or placebo (one tablet) to be taken orally in the evening. This will be up-titrated at Visit 2 (week 4) to 80mg (two tablets) if all safety parameters have been met at visit 2.

Participants will be allocated one bottle each containing 220 tablets for the duration of the study. There will therefore be one drug dispensation at baseline and the patient will be reminded to up titrate after one month at Visit 2.

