15.1 Definitions

Table 1: Adverse Event Definitions

Adverse Event (AE)	Any untoward medical occurrence in a patient or clinical trial participant administered a medicinal product and which does not necessarily have a causal relationship with this treatment. Therefore an AE can be any unfavourable or unintended change in the structure (signs), function (symptoms) or chemistry (laboratory data) in a participant to who an IMP or procedural intervention has been administered, including occurrences which are not necessarily caused by or related to that product.
Adverse Reaction (AR)	Any untoward and unintended response in a participant to an investigational medicinal product which is related to any dose administered to that participant. This includes medication errors, uses outside of protocol (including misuse and abuse of product)
Serious Adverse Event (SAE), Serious Adverse Reaction (SAR) or Unexpected Serious Adverse Reaction	Any adverse event, adverse reaction or unexpected adverse reaction, respectively, that: 
 • results in death, • is life-threatening*, • requires hospitalisation or prolongation of existing hospitalisation**,

	
 • results in persistent or significant disability or incapacity, or • consists of a congenital anomaly or birth defect 
*A life- threatening event, this refers to an event in which the participant was at risk of death at the time of the event; it does not refer to an event which hypothetically might have caused death if it were more severe.
 
** Hospitalisation is defined as an in-patient admission, regardless of length of stay. Hospitalisation for pre-existing conditions, including elective procedures do not constitute an SAE."

	
*A life- threatening event, this refers to an event in which the participant was at risk of death at the time of the event; it does not refer to an event which hypothetically might have caused death if it were more severe.
 
** Hospitalisation is defined as an in-patient admission, regardless of length of stay. Hospitalisation for pre-existing conditions, including elective procedures do not constitute an SAE.

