15.2 Recording adverse events

All adverse events following IMP administration will be recorded in the medical records in the first instance. As simvastatin is a licensed product with a well-established safety profile, AEs that are non-serious or MS related (see section 15.5 for MS expected adverse events) will be recorded in the source data (Medical records and Participant diary cards) only.

All adverse events will be recorded with clinical symptoms and accompanied with a simple, brief description of the event, including dates as appropriate.

Clinically significant abnormalities in the results of objective tests (e.g. laboratory variables) will also be recorded as adverse events in the medical notes and if assessed as serious they will also be recorded on the SAE log and in the CRF. If these events are not expected as part of disease or IMP, these will be recorded as unexpected.

All adverse events will be recorded until 6 weeks after the participant's final clinical visit (EOS).

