Appendix 1 - schedule of assessments

Visits	Visit 0 Pre- screening	Visit 1* (Combined Screening/ Baseline)	Visit 2	Visit 3* (End of Study Treatment Visit)	Visit 4* (End of Study Follow-up)	Unscheduled (inc. relapse if indicated)	Telephone / e-mail Follow Up
Visit Windows (1 week is equivalent to 7 days e.g. 4 weeks (1 month) is equivalent to 28 days)	within 8 weeks	Day 0	Week 4 (+1 week)	Week 16 (+1 week)	Week 20 (+2 weeks)	Between V1 to EOS Follow-up	As required
Pre-screening questionnaire	X						
Inclusion/Exclusion criteria review	X	X					X
Informed consent		X					
Medical history		X					
Con-meds		X	X	X	X	X	X
Medical review ¹		X	X	X	X	X	X
Recording of AEs			X	X	X	X	X
Physical examination		X	X	X	X	X	
Vital Signs		X	X	X	X	X	
Disability Assessment (EDSS)		X		X	X	X	
MSFC (9HPT, 25TFW)		X		X	X		
SDMT		X		X	X		
FAB		X			X		
MSIS-29v2		X		X	X		
MSWSv2		X		X	X		
EQ5D5L		X		X	X		

Visits	Visit 0 Pre- screening	Visit 1* (Combined Screening/ Baseline)	Visit 2	Visit 3* (End of Study Treatment Visit)	Visit 4* (End of Study Follow-up)	Unscheduled (inc. relapse if indicated)	Telephone / e-mail Follow Up
Visit Windows (1 week is equivalent to 7 days e.g. 4 weeks (1 month) is equivalent to 28 days)	within 8 weeks	Day 0	Week 4 (+1 week)	Week 16 (+1 week)	Week 20 (+2 weeks)	Between V1 to EOS Follow-up	As required
Safety bloods (see section 11.1 for list of laboratory tests)		X	X	X	X	X	
Urine pregnancy test ⁴		X		X	X		
Immunology and biomarkers		X	X	X	X		
MRI		X		X	X		
ASL questionnaire		X					
ASL questionnaire follow-up				X	X		
Visual assessment		X					
Retinal Imaging Vascular Assessment Questionnaire		X		X	X		
Advanced retinal imaging inc. OCT*		X		X	X		
Randomisation		X					
Drug dispensed ³		X (40mg)					
Drug uptitration ³			X (80 mg)				
Drug Diary issued		X					
Confirmation to dose ²		X					
Drug accountability (diary) ⁵			X	X			
Drug compliance ⁵			X	X			X
Telephone contact							X

^{*} This visit will take place across two sites. The assessments may be split across two days. Day 1 assessments will take place at the UCL Institute of Neurology & National hospital for neurology and neurosurgery and day 2 assessments (visual assessment and Advanced Retinal Imaging) will take place at Moorfields Eye Hospital. Patients will be dispensed the drug on Day 1 of visit 1 but will be instructed not to take the drug until the evening of Day 2 of visit 1 (if over 2 days) after all ophthalmic assessments are completed. See Section 10 for full details.

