¹ This will encompass any medical or MS-related symptoms that have arisen between Visit 1 and subsequent visits.

² Study medication must only be dispensed after randomisation once all day 1 of visit 1 assessments have been completed and the relevant safety reports have been obtained. Patients will be dispensed the drug on Day 1 of visit 1 but will be instructed not to take the drug until the evening of Day 2 (if over 2 days) of visit 1 after all ophthalmic assessments are completed. See Section 10 for full details.

³ Participants will be allocated 220 tablets each for the duration of the study. There will therefore be one drug release at baseline and the patient will be reminded to uptitrate after one month at Visit 2. The patient will take 40mg x 2 tablets for the dose of 80mg for a period of 12 weeks. The neurologist will issue the drugs, diary and record compliance at the relevant visits.

For the purpose of safety, the study participant will be contacted by telephone and adverse events assessed by the neurologist. If there are no issues identified, the participant will be advised to take the study medication and encouraged to contact a member of the research team if problems subsequently arise.

⁴ For female subjects only

⁵ This will include a drug diary review and pills count.

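### Protocol 15.4 ties the start of SAE recording to a drug release at Visit 2, though the only release is at Visit 1; 15.2, 15.4 and 15.5 also disagree on when recording ends and what enters the CRF

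*Protocol*

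**What the plan says.** **Start.** Protocol 15.4 states: "All SAEs will be recorded from the time of the first enrolled participant's drug release (at Visit 2) until 6 weeks post-treatment". On dispensing, section 9.2 says "Randomisation and drug dispensation will take place on day 1 of visit 1" and section 10.1 says "There will therefore be one drug dispensation at baseline". Appendix 1 says "Patients will be dispensed the drug on Day 1 of visit 1" and, in footnote 3, "There will therefore be one drug release at baseline"; its grid marks dispensing at Visit 1 only. The drug step listed for Visit 2 in section 9.3.1 is "Uptitration of drug at 80mg dose". Section 15.2 has its own start for adverse events in general: "All adverse events following IMP administration will be recorded in the medical records in the first instance".

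**End.** Section 15.2 records all adverse events up to 6 weeks after the last clinical visit, which it labels EOS. Section 15.4 records SAEs up to 6 weeks after treatment ends. A later sentence of 15.4 has SAEs reported to the sponsor until the trial ends, which 14.7 defines as completion of the immune and biomarker sample analysis. Section 15.1 defines an SAE as "Any adverse event, adverse reaction or unexpected adverse reaction, respectively, that" meets one of the listed seriousness criteria, so every SAE is also an adverse event under 15.2.

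**CRF.** Section 15.2 confines adverse events that are either non-serious or MS-related to the medical records and diary cards, and refers the reader to 15.5. Section 15.5 has symptoms of MS progression entered in the notes and the CRF, without an SAE form. The opening sentence of 15.4 puts every serious event in the medical records, the CRF and the SAE log.

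**The concern.** These are operating instructions for safety data, and they conflict in three places. The visit named in 15.4 is not the visit at which drug is released. The AE and SAE rules give different end dates for events that fall under both. The cross-reference from 15.2 to 15.5 leads to the opposite CRF rule.

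What is at stake is consistency. Two members of staff following different sections could treat the same event differently: inside or outside the SAE window, in or out of the CRF. Any comparison of adverse events by arm needs one defined window and one rule on which events reach the database. The end-date question is sharpest for participants who stop treatment early, because 14.2 keeps them in the trial for follow-up.

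**Working it through.** No power or sample-size figure is involved. The check is a comparison of text plus addition of visit weeks.

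**Inputs (sections 9.2–9.3.3 and Appendix 1).** Visit 1 = day 0. Visit 2 = week 4 (+1), so weeks 4–5. Visit 3, end of treatment = week 16 (+1), so weeks 16–17. Visit 4, follow-up = week 20 (+2), so weeks 20–22.

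**The plan's own duration.** 16 + 1 = 17 weeks on treatment and 20 + 2 = 22 weeks in total. Both match the structured summary in section 2.1.

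**Is there only one release?** Tablets needed at one a day for 28 days and two a day for 84 days: 28 + 2 × 84 = 196. With Visit 3 a week late: 28 + 2 × 91 = 210. The single bottle holds 220, so the supply fits one release at Visit 1.

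**Start of SAE recording under 15.4, three readings:**
- Drug release governs: the start is Visit 1 and 0 weeks are lost.
- The Visit 2 label is applied to each participant: 4/17 = 23.5% to 5/16 = 31.3% of treatment weeks precede the SAE-specific window.
- One trial-level date, set by the first enrolled participant, with the Visit 2 label followed: only those enrolled in the first 4–5 weeks could be affected. At the projected 3–4 recruits a month (section 22.2), with 4 weeks to a month as in Appendix 1, that is about 3 × 4/4 = 3 to 4 × 5/4 = 5 participants.

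**End, treatment completers:**
- 15.2, EOS = Visit 4: 20 + 6 = 26 to 22 + 6 = week 28.
- 15.4: 16 + 6 = 22 to 17 + 6 = week 23.
- Difference within a participant = Visit 4 − Visit 3: 20 − 17 = 3 to 22 − 16 = 6 weeks.
- If EOS means Visit 3, the difference is 0.

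**End, a participant who stops at Visit 2, does not restart, and stays in follow-up:**
- 15.4: 4 + 6 = 10 to 5 + 6 = week 11.
- Difference if EOS = Visit 4: 20 − 5 = 15 to 22 − 4 = 18 weeks.
- Difference if EOS = Visit 3: 16 − 5 = 11 to 17 − 4 = 13 weeks.

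Section 10.2 limits that last case. Participants withdrawn at week 4 because they could not tolerate 40 mg are approached again at week 12 about restarting. One who restarts and continues to Visit 3 returns to the completer range of 3–6 weeks. But a 15.4 window counted from the first stop would close at weeks 10–11, before the week-12 approach, and the protocol does not define the end of treatment for someone who restarts.

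**CRF rule, side by side:**
- Non-serious symptom of MS progression: medical records and diary only under 15.2; notes and CRF under 15.5.
- Serious MS-related event: medical records and diary only under 15.2; CRF under both 15.4 and 15.5.

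Section 20.2 says paper CRFs serve as source documents. That softens the conflict but does not remove it, because 15.2 names two source documents and the CRF is neither of them.

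**The case against.** The strongest reply is that the Visit 2 label is an evident slip, since Appendix 1 uses the same term, release, for the baseline dispensing, and that other provisions protect SAE capture. Much of this stands. Section 15.2 covers adverse events from IMP administration onwards. The opening sentence of 15.4 has no start date. SARs and SUSARs are reportable however late they occur, and 15.6 requires all deaths to be reported. A reader might infer that SAEs in the first month go unrecorded; the documents do not support that.

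A reader might also take 24–31% of treatment time as unprotected. That needs the label to be applied to each participant, and the text refers to the first enrolled participant. Nor is 15–18 weeks a general figure for early stoppers: it requires a stop at Visit 2, no restart and continued follow-up. Section 14.2 keeps such participants in for safety and/or data analysis, so attendance at Visit 4 is not certain.

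On the end date, SAEs other than the 15.5 events go to the sponsor on an SAE form until the trial ends, and filling in that form is itself a record. This largely closes the practical gap for those events. It also adds a further date that 15.4 does not reconcile with its own recording window.

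One could read 15.2 and 15.4 as two tiers, notes for AEs and log for SAEs, but neither section says so. The sponsor SOP (INV/S05) and the SAE flow chart in 15.4.1 may settle some of this. Neither could be checked, so divergent practice at site is possible but not shown.

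**Conclusion.** The contradictions are real and in current text, but minor. The visit label in 15.4 is wrong on any reading, and the per-participant start is unstated. The AE and SAE end dates differ by 3–6 weeks for completers if EOS means Visit 4 and by 0 if it means Visit 3. The phrase used in 15.2, the participant's last clinical visit, points to Visit 4, but both visits carry End of Study in their titles. The difference of 15–18 weeks (11–13 if EOS means Visit 3) applies only under the three conditions given above. The CRF conflict between 15.2 and 15.5 is direct; the conflict with 15.4 concerns MS-related events that are serious.

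No SAE is shown to be lost, and the primary CBF analysis is untouched. Section 23.2 promises details of adverse event analyses that the SAP does not give. That is a separate omission and adds no weight here.

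**What to change.** 1. In 15.4, correct the visit label so that SAE recording starts at each participant's own drug release at Visit 1.
2. Reconcile the recording end dates in 15.2 and 15.4 with each other and with the sentence on reporting to the sponsor until the trial ends. Name the visit meant by EOS, and say how the rule applies to participants who stop early and to those who restart at week 12.
3. Reconcile 15.2 with 15.4 and 15.5 on whether MS-related events, serious and non-serious, enter the CRF.
4. Check that INV/S05 and the flow chart in 15.4.1 agree with the reconciled text.

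The cost is wording in three sections. No new assessment is needed, and the choice in 15.2 to keep other non-serious events in source can stay. If the later end date is adopted, recording under 15.4 runs 3–6 weeks longer for completers and longer for early stoppers. It would then run to weeks 26–28, past the last scheduled visit and the stated 22 weeks per participant, so the text should also say how events in that period are to be ascertained.

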15.4.1 Flow Chart for SAE reporting

15.5 Serious Adverse Events which do not require immediate reporting

SPMS and PPMS are progressive neurological conditions and as such deterioration in neurological symptoms is expected. Symptoms of MS disease progression will be RECORDED in the participants' medical notes and in the CRF. However, SAE forms will not be completed and sent to the sponsor. The following SAEs are deemed as symptoms of MS disease progression and do not require immediate reporting:

- natural changes in motor, sensory, balance, sphincter (including urinary tract infections), visual, cognitive and fatigue levels

Symptoms of disease progression will be graded as follows:

Grade 1 relapse: relapse not treated with corticosteroids

Grade 2 relapse: relapse treated with corticosteroids, but not requiring hospitalisation

Grade 3 relapse: relapse treated with corticosteroids and requiring in-patient hospitalisation; or relapse not treated with corticosteroids but requiring in-patient hospitalisation

If the participant feels they are experiencing a relapse, they should contact their local MS team (nurse/consultant) or General Practitioner as per routine practice, so that appropriate management can occur. They should also inform the study team at their next scheduled visit, so that the relapse can be documented. At the Investigator's/nurse's discretion the patient can attend for an unscheduled visit, see section 9.3.4.

If the frequency or severity of these symptoms is not consistent with the SPC or disease the event must be reported to the sponsor as an SAE in the normal way

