Simvastatin	fatal and non fatal hepatic failure)	Very rare	Patient will have liver function tests performed prior to study entry and whilst on study to monitor their Hepatic function. Patients with known Hepatic failure, who consume substantial quantities of alcohol and/or have screening Liver function test > 3XULN will be excluded from the study. If

			patients whilst on study have LFTs > 3XULN or present with clinical symptoms of liver injury, then, at the discretion of the treating clinician, simvastatin will be discontinued.
Simvastatin	Myopathy/ Rhabdomyolysis	Rare	
Simvastatin occasionally causes myopathy manifested as muscle pain, tenderness or weakness with creatine kinase (CK) above ten times the upper limit of normal (ULN). The risk of myopathy is greater in patients on simvastatin 80 mg. The risk of myopathy and rhabdomyolysis is also significantly increased by concomitant use of simvastatin with certain medications and supplements such as potent inhibitors of CYP3A4, Fibrates, grapefruit juice, Calcium Channel Blockers (see section 7.5 for full list of medications). Myopathy sometimes takes the form of rhabdomyolysis with or without acute renal failure secondary to myoglobinuria, and very rare fatalities have occurred.
 
Patient's plasma renal function will be tested at screening and monitored whilst on study. Patients with known renal failure and or plasma potassium exceeds 5.5mmol/l or plasma sodium <125mmol/l or creatinine>130mmol/l, will be excluded. If these parameters are breached during the trial, patient will be monitored as per routine best medical practice and at the discretion of the treating clinician, simvastatin dose may be reduced or discontinued.
 
Potassium conserving drugs and potassium supplements are also prohibited (see section 7.5).
 
Patients who are on medications that interact with Simvastatin and increases the risk of myopathy (see list in section

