Simvastatin	Insomnia	Very Rare	Symptoms will be monitored and treated at the discretion of the treating clinician as per routine best medical practice.
	Cognitive / memory impairment	Very rare	There have been rare post-marketing reports of cognitive impairment (e.g. memory loss, forgetfulness, amnesia, memory impairment, confusion) associated with statin use. The reports are generally nonserious, and reversible upon statin discontinuation, with variable times to symptom onset (1 day to years) and symptom resolution (median of 3 weeks). Symptoms will be monitored and treated at the discretion of the treating clinician as per routine best medical practice.
Simvastatin	Headache, paresthesia, dizziness or peripheral neuropathy.	Rare	Symptoms will be monitored and treated at the discretion of the treating clinician as per routine best medical practice. Simvastatin has no or negligible influence on the ability to drive and use machines. However, when driving vehicles or operating machines, it should be taken into

			account that dizziness has been reported rarely in post-marketing experiences and the patient information sheet will explain this rare risk and caution.
Simvastatin	Skin and Subcutaneous disorders (e.g. rash, pruritus, alopecia)	Rare	Symptoms will be monitored and treated at the discretion of the treating clinician as per routine best medical practice.
Simvastatin	Pregnancy	Not Known	Safety in pregnant women has not been established and it is not known whether simvastatin or its metabolites are excreted in human milk. Women who are pregnant or breast feeding will be excluded. Women of Child bearing potential will need to agree to use adequate contraception and will have a urine pregnancy test to confirm they are not pregnant prior to being enrolled.

The table below summarise the risks and mitigations of all tests above standard care that are being performed:

Intervention	Potential risk	Risk Management

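### The MS-progression exemption in protocol 15.5 removes the 24-hour SAE form without a relatedness condition, and its escape clause treats consistency with the SPC as a reason not to report

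*Protocol*

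**What the plan says.** Section 15.5 of the protocol defines the exemption: "The following SAEs are deemed as symptoms of MS disease progression and do not require immediate reporting". The list that follows is "natural changes in motor, sensory, balance, sphincter (including urinary tract infections), visual, cognitive and fatigue levels". The consequence is stated as "However, SAE forms will not be completed and sent to the sponsor". The progression grading in the same section runs up to relapses needing in-patient admission, so the exemption reaches events that are serious by hospitalisation.

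Section 15.4 repeats the exception in its reporting rule: "All SAEs (except those specified in section 15.5 as not requiring reporting to the Sponsor".

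The way back into reporting is the last sentence of 15.5: "If the frequency or severity of these symptoms is not consistent with the SPC or disease the event must be reported to the sponsor".

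The risk table in section 4 says "Simvastatin occasionally causes myopathy manifested as muscle pain, tenderness or weakness", with greater risk at 80 mg, and "There have been rare post-marketing reports of cognitive impairment". It also lists paraesthesia, dizziness and peripheral neuropathy as rare risks.

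Other provisions bear on the point:
- 15.3 requires causality to be assessed for each adverse event.
- 15.4 says serious adverse reactions (SARs) and SUSARs must be reported to the sponsor however late they occur.
- 15.4 sends all serious events to the CRF and to an SAE log that goes to the sponsor at least once or twice a year.
- 15.6 requires immediate reporting of all deaths.
- 15.2 keeps adverse events that are non-serious or MS-related in source data only.

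**The concern.** An exemption for disease progression is reasonable in progressive MS, but it should be limited to events thought not to come from the drug. Here it is defined by symptom domain alone, and several of those domains are ones in which the protocol expects simvastatin to cause harm. Staff are blinded and the population is expected to worsen, so new weakness or cognitive decline has a ready alternative explanation.

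The escape clause adds to the difficulty. Consistency with the SPC properly informs expectedness, which separates a SUSAR from an expected SAR. It is not a reason to withhold an SAE form. What is at stake is how soon the sponsor hears of a serious event that could be either MS or a reaction to the drug.

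**Working it through.** No arithmetic in the plan is in dispute, so the check sets the provisions side by side.

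**Step 1. Overlap of the exempt domains with section 4**

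| Exempt domain (15.5) | Simvastatin risk in section 4 |
|---|---|
| Motor | Myopathy presenting as weakness |
| Cognitive | Cognitive or memory impairment |
| Sensory | Paraesthesia, peripheral neuropathy |
| Balance | Dizziness |
| Visual, sphincter, fatigue | None listed |

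Four of the seven domains overlap. The SPC is not among the documents, so section 4 stands in for it.

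**Step 2. What the escape clause returns to reporting**

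The wording can mean consistent with neither the SPC nor the disease (reading A), or inconsistent with at least one of them (reading B).

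| Consistent with SPC | Consistent with MS | Reading A | Reading B |
|---|---|---|---|
| Yes | Yes | No form | No form |
| Yes | No | No form | Report |
| No | Yes | No form | Report |
| No | No | Report | Report |

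On reading A, an event that matches the SPC but is atypical for MS gets no form. On reading B that event is reported. But the only events left without a form are then those matching both, while typical MS symptoms that do not match the SPC would need one, which is the reverse of the exemption's purpose. On both readings, the event that resembles both MS and a listed reaction gets no form through this clause.

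**Step 3. How causality interacts with the exemption**

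Section 15.3.2 has six categories, and the protocol does not say which of them make an event related for the SAR rule in 15.4.

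| Causality | SAR rule in 15.4 | Exemption in 15.5, if a listed symptom |
|---|---|---|
| Definitely, Probably | Reportable | Exempt as worded |
| Possibly | Unclear | Exempt as worded |
| Not Assessable | Unclear | Exempt as worded |
| Unlikely, Not related | Not a SAR | Exempt |

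For the first row the SAR sentence carries no exception for 15.5, so it can fairly be taken to prevail. For Possibly and Not Assessable nothing settles the matter. Section 15.3.2 also ties the causality judgement to completion of the case report form, not to the decision to apply the exemption.

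**Step 4. Where an exempt event is recorded**

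| Section | Destination |
|---|---|
| 15.2 | MS-related events: source data only |
| 15.4 | All serious events: medical records, CRF and SAE log |
| 15.5 | Progression symptoms: medical notes and CRF |

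These three rules do not agree. If 15.2 is followed, the event may not reach the log.

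**Step 5. Length of the delay**

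Assume the log is evenly spaced. Sent twice a year, the interval is 52 / 2 = 26 weeks; sent once, 52 weeks. Treatment lasts up to 17 weeks and participation 22 weeks. The sponsor could therefore first see an exempt event after that participant has left the trial.

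**The case against.** The strongest reply is that the protocol already covers drug reactions. A SAR is reportable under 15.4 whether or not the SPC lists it, and causality must be assessed for every event. The exemption is limited to natural changes that are symptoms of MS progression, and a statin reaction is neither. Exempt events stay in the CRF and the periodic log, and deaths are always reported. Creatine kinase (CK) monitoring gives an independent route to myopathy.

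Much of this stands, and it rules out several stronger readings:
- A reader might infer that serious simvastatin reactions go unreported. The documents do not support that. An event judged related is a SAR, and under 15.4 and 15.5 an exempt event is still recorded. The loss is of the 24-hour form.
- A reader might infer that the escape clause always fails for reactions listed in the SPC. That is true only on reading A.
- A reader might infer that no causality assessment exists. It does, in 15.3. What is missing is any link that makes it a condition of the exemption.
- A reader might extend the overlap to fatigue. Section 4 does not list fatigue as a simvastatin risk.

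The reply does not close the gap. The SAR rule protects only events already judged related, and natural change is not defined. CK does not detect cognitive, sensory or balance reactions. Scheduled safety bloods are at baseline and weeks 4, 16 and 20, so 16 − 4 = 12 weeks pass between the up-titration visit and the next scheduled CK. CK at unscheduled visits depends on one taking place. There the protocol is also inconsistent: 9.3.4 asks participants who suspect a relapse to contact the study team between visits, while 15.5 sends them to their local MS team or GP and has them tell the study team at the next scheduled visit.

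**Conclusion.** The concern holds in limited form. Section 15.5 has no relatedness condition, its escape clause is ambiguous and points the wrong way on the SPC, and 15.2, 15.4 and 15.5 disagree on recording. The effect is loss of expedited reporting for serious motor, sensory, balance or cognitive events that resemble both MS and a listed reaction, especially those scored Possibly or Not Assessable.

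No frequency can be given, because the documents contain no rate for such events. For scale only, one event in a planned arm of 20 is 1/20 = 5% of that arm; this is not a risk estimate. The delay is about 26 to 52 weeks if the log works as 15.4 describes, and undefined if 15.2 is followed instead.

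The conclusion assumes that section 4 reflects the relevant SPC content and that the SAR sentence in 15.4 overrides the exemption for events judged related. If it does not, the gap is wider. The point should be corrected but does not threaten the trial's primary analysis.

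**What to change.** 1. Add to 15.5, and mirror in the 15.4 exception: *The exemption applies only when causality under 15.3.2 has been assessed, before the exemption is used, as Unlikely or Not related. Events assessed as Possibly, Probably, Definitely or Not Assessable are reported as SAEs within 24 hours.*
2. Remove the SPC from the escape clause, so that it asks only whether frequency or severity is consistent with the disease.
3. Reconcile 15.2, 15.4 and 15.5 on whether serious MS-related events go to source data only, to the CRF, or to the CRF and the SAE log. Reconcile 9.3.4 and 15.5 on whom participants contact when they suspect a relapse.

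The cost is a short amendment and a few more SAE forms among 40 participants. The causality assessment is already required, so the added work is making it before the exemption is used. The change does not remove all of the risk: an event confidently misattributed to MS would be scored Unlikely or Not related and would still be exempt.
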